We posit that practices that have more highly developed PA&E and better teamwork will more effectively activate patients with diabetes and/or CVD. In turn, we posit that more highly activated patients will be more likely to achieve improvements on patient-reported outcomes, patient care experiences, and clinical measures over time compared to less activated patients. We also will also examine the roles that patient advisory groups and primary care team use of performance feedback data play in influencing improvements in patient activation and outcomes of care over time.

Figure 1. Logic Model

We will engage patients and primary care practice teams within two accountable care organizations (ACOs). In each ACO, we will randomly select eight practices: four who score high on PA&E activities and four who score low. We will survey practice team members twice: once at baseline and one a year later. We will also conduct two site visits: one near the beginning of the study and one during the 13-18 month period of the study.

[figure not shown]
We will randomly select four high and four low PA&E sites within each ACO using a broad definition of PA&E activities including: (1) patient care outreach in regard to disease prevention and health promotion; (2) changes in the clinician-patient relationship, particularly in the areas of communication, motivational interviewing, and patient involvement in treatment care plans; (3) shared decision-making; (4) patient self-management of their condition(s); (5) end of life/advanced serious illness care patient engagement and family involvement; and (6) patient involvement in the overall design of care and in organization-wide efforts to improve the quality of care. See methods section for a description and Appendix I for an example of the instrument to be used for determining the “more highly involved” and “less highly involved” practices.

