ACO Established	MSSP: July, 2012 AdvocateCare (Commercial): 2011	MSSP: January, 2014 Cigna (Commercial): April, 2013 Anthem (Commercial): July 2013
Location	Illinois	Senior ACO (MSSP): CA, FL, NV Commercial ACO: Greater Los Angeles, CA, NV (Cigna)
Patient population	MSSP: 106,000 Commercial: 370,000	Senior (MSSP): 56,689 Commercial: 65,739
ACO Contract Lives	MSSP: 106,000 Commercial: 370,000	Senior (MSSP): 56,689 Commercial: 65,739

PRINCIPAL INVESTIGATOR (LAST, FIRST, MIDDLE): [name]

Patient Race/Ethnicity	57% Non-Latino White 22% African American 8% Latino 5% Other/multi-racial 3% Asian/Filipino 1% American Indian/Alaska Native 1% Middle East 1% Eastern Indian 2% Unknown/Declined	
 55% Latino 25% Non-Latino White 15% Asian/Pacific Islander 10% African-American 	CLINIC/PRACTICE SELECTION Advocate ACO and HealthCare Partners ACO have 150 and 69 primary care practice sites, respectively. Using the list of PA&E activity domains previously described (see Appendix I for a draft of the checklist instrument), we will randomly select four practices from each ACO that score in the top quartile of the PA&E activities and four practices from each ACO that score in the bottom quartile. This will maximize the difference between those practices with high involvement and those with little or no involvement.
Payer Mix	
 Commercial: 70% Medicare Advantage: 5% Advocate Employee: 5% Medicare ACO: 20% 	
 HCP commercial: 68% HCP Medicaid: 13% HCP Senior: 19% 	
ACO Risk Arrangement	
 Shared savings (no risk) 	
 Shared savings (no risk) 	

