We will categorize the more than 150 Advocate ACO primary care practice sites and the 69 HCP ACO practice sites as high vs. low PA&E involvement based on a brief 40-item practice assessment of the six domains of PA&E activities (see Appendix I). This list was developed in consultation with a National Advisory Committee to our study of ACO involvement in PA&E and the preliminary results of the survey (see page 2) supported by the Gordon and Betty Moore Foundation. This checklist instrument, including measures of the degree of implementation, will be completed by the person most knowledgeable about each practice's PA&E activities. Based on past experience this will be the Chief Medical Officer or Quality Improvement leader. Each of the ACOs practices will be categorized into quartiles based on their overall PA&E score. We will then sample practices for involvement from the top and bottom quartiles to finalize four highly involved PA&E practices and four low involved PA&E practices within each of the two ACOs for engagement in the research study.

Patient Activation (PAM)

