Analyses Addressing Aim 1. At each of the two cross-sections for the patient and teamwork assessment surveys, we will clean the data, examine their distributions, and conduct psychometric analysis to assess the reliability and validity of the measures. After composite variables have been constructed and properties assessed, we will examine the cross-sectional relation of PA&E activities, teamwork assessment results, and patient survey results. Using a dichotomized variable derived from baseline responses to the PA&E Practice Site Assessment Survey (see Appendix I), we will categorize sites as “high” or “low” PA&E based on the response distributions in our data. We will then assess association of key measures in two stages. In the first equation, using linear regression models, we will examine the PAM as a function of high vs. low PA&E (site level), controlling for practice size, and for patient casemix adjustment variables previously used in research that has compared organizations on patient experience and clinical quality measures^{79, 80}. Casemix factors to be considered include age, sex, educational attainment, and comorbid health conditions. We will then examine the patient reported outcome (PRO) measures, patient experience (PE) and the clinical measures as a function of the PAM, PA&E level (at site level), practice size, and casemix using multilevel regression models to account for the clustering of patients within practices. The simplified equations are:

$$PAM = Hi / lowPA \& E + PracticeSize + Casemix + \epsilon$$

$$PE = Hi / lowPA \& E + PAM + PracticeSize + Casemix + \epsilon$$

$$PRO = Hi / lowPA \& E + PAM + PracticeSize + Casemix + \epsilon$$

$$ClinMeasures = Hi / lowPA \& E + PAM + PracticeSize + Casemix + \epsilon$$

Aim 2. To assess whether the relation of PA&E activities and better PROs and clinical outcomes is stronger for more highly activated patients than less activated patients at baseline.

Analyses Addressing Aim 2. To address the extent to which PA&E activities conducted by the practice are more influential in improving PROs and patient experience among patients with high PAM levels at baseline, we will extend the Aim 1 analyses. Specifically, we will use multilevel regression with site random effects to model changes in PROs and the clinical measures over time as a function of baseline PAM scores, practice size, patient casemix, PA&E, and then by interacting PA&E and the PAM scores. The simplified equations are:

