$$PE = Hi / lowPA \& E + PracticeSize + PAM + PA \& E * PAM + Casemix + \epsilon$$

$$PRO = Hi / lowPA \& E + PracticeSize + PAM + PA \& E * PAM + Casemix + \epsilon$$

$$ClinMeasures = Hi / lowPA \& E + PracticeSize + PAM + PA \& E * PAM + Casemix + \epsilon$$

We will explore differences between the two extreme PAM categories (level 1=lowest activation, 4=highest activation) in addition to examining the continuous PAM measures, as we expect the biggest differences over time differences in PRO and patient experience between patients with highest and lowest baseline PAM scores.

PRINCIPAL INVESTIGATOR (LAST, FIRST, MIDDLE): [name]

Aim 3. To assess the stability of the PA&E-outcome relationship over two measurement periods at the individual and practice-level;

Analyses addressing Aim 3. After both waves of data collection are completed, we will assess the consistency of the results at two levels- patient-level and practice-level. We will compare the regression coefficients for models at each wave to examine differences in associations of the independent variables with outcomes at each cross-section.

Aim 4. To assess changes over time (T1 vs. T2) in patient-reported outcomes of care, patient experience and clinical measures, as a function of changes over time in PA&E activities, patient activation, controlling for patient casemix.

Analyses Addressing Aim 4. We will integrate the patient survey results and the patient level results at the practice level. We will examine 'over time' effects using three approaches: 1) multilevel regression with interaction term as specified here, 2) stratified by low vs. high PA&E practices and looking at coefficient differences, 3) lagged regression (using T1 to predict T2) vs. change in T1 and T2 predicting T2), etc. The simplified equations below provide a multilevel framework for studying the impact of site PA&E activities on patient activation, patients' experiences, and patient-reported outcomes over time:

$$\Delta PRO = \Delta PA \& E + \Delta PAM + \varepsilon$$

$$\Delta PE = \Delta PA \& E + \Delta PAM + \varepsilon$$

$$\Delta ClinMeasures = \Delta PA \& E + \Delta PAM + \varepsilon$$

Given the uncertainty in distribution and variation, we will examine the inclusion of other relevant predictors including fixed effects for casemix and practice size.

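### The Aim 1 outcome models do not name ACO, the stratum used to select practices; if an ACO gap in outcome levels remains, the high-low comparison loses power that one covariate would keep

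*Combined protocol and SAP*

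**What the plan says.** **Selection.** ACO is the stratum. The Research Plan states: "In each ACO, we will randomly select eight practices: four who score high on PA&E activities and four who score low". Clinic/Practice Selection adds: "we will randomly select four practices from each ACO that score in the top quartile of the PA&E activities", with the same number from the bottom quartile. Measurement of Site PA&E Activities ends with "four highly involved PA&E practices and four low involved PA&E practices within each of the two ACOs".

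**Analysis.** In the Analysis Section, the Aim 1 models for patient-reported outcomes, patient experience and clinical measures use PAM, "PA&E level (at site level), practice size, and casemix using multilevel regression models to account for the clustering of patients within practices". On covariates: "Casemix factors to be considered include age, sex, educational attainment, and comorbid health conditions". The high/low variable comes from the baseline practice survey: "we will categorize sites as “high” or “low” PA&E based on the response distributions in our data". For Aim 3: "We will compare the regression coefficients for models at each wave". For Aim 4, whose equations hold only the changes in PA&E and PAM: "we will examine the inclusion of other relevant predictors including fixed effects for casemix and practice size".

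Neither the equations for Aims 1 to 4 nor the prose around them names ACO. The equations are described as simplified and the covariate lists are open, so ACO is unplanned rather than ruled out.

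**The concern.** A comparison of 8 with 8 practices rests mainly on practice-level error. When practices are selected within strata, the model normally carries the stratum, so that differences between strata do not count as noise. Here any difference in outcome level between the two ACOs that PAM, casemix and practice size leave unexplained would be read as ordinary practice-to-practice variation. The high-low estimate hardly moves, but its reported standard error grows, and a real difference may be missed or reported with too wide an interval.

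A gap is possible. The Latino share is 8% at Advocate and 55% at HealthCare Partners, and the section on the impact of the condition says Latino patients reach glycemic, cholesterol and blood pressure goals less often. Ethnicity, language, payer and region are not in the listed casemix.

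**Working it through.** **Inputs from the documents.** 16 practices, 4 in each ACO-by-PA&E cell; 273 patients sampled per practice; 3% undeliverable; response 50% at wave 1 and 65% at wave 2; 20% dropout; ICC 0.01 to 0.04 for PROMIS; minimally important difference 0.20 SD for PROMIS physical function.

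**Assumptions.** Two-sided alpha 0.05 (not stated); t-test on practice-level degrees of freedom (no method stated); ACO gap g of 0, 0.05, 0.1 or 0.2 patient-level SD (none given).

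**Step 1: the plan's own sample.** 4,368 × 0.97 × 0.50 × 0.65 × 0.80 = 1,101.6, or 68.9 per practice. This reproduces the stated 1,102 and 69. The wave 1 cross-section that Aim 1 uses is larger: 273 × 0.97 × 0.50 = 132.4, so m = 132 per practice.

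**Step 2: effect on the standard error.** The variance of a practice mean is V = ICC + (1 − ICC)/m.
- ICC 0.01: 0.01 + 0.99/132 = 0.0175
- ICC 0.04: 0.04 + 0.96/132 = 0.0473

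An omitted gap adds 16 × (g/2)² = 4g² to the practice-level sum of squares. On 14 degrees of freedom that is (4/14)g². The ratio of reported standard errors, without ACO to with it, is about √(1 + (4/14)g²/V). For g = 0.1 and ICC 0.01 this is √(1 + 0.00286/0.0175) = 1.08.

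**Step 3: power at wave 1.** Simulation with 40,000 draws, effect 0.20 SD, a practice-size covariate in the model, 13 df without ACO and 12 with it:

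| ICC | Gap (SD) | Ratio, formula | Ratio, simulated | Power without ACO | Power with ACO |
|---|---|---|---|---|---|
| 0.01 | 0 | 1.000 | 0.996 | 77.1% | 76.3% |
| 0.01 | 0.05 | 1.020 | 1.016 | 75.8% | 76.3% |
| 0.01 | 0.1 | 1.078 | 1.073 | 72.0% | 76.3% |
| 0.01 | 0.2 | 1.286 | 1.278 | 56.9% | 76.3% |
| 0.04 | 0 | 1.000 | 0.997 | 38.1% | 37.6% |
| 0.04 | 0.05 | 1.008 | 1.004 | 37.6% | 37.6% |
| 0.04 | 0.1 | 1.030 | 1.026 | 36.0% | 37.6% |
| 0.04 | 0.2 | 1.114 | 1.110 | 30.2% | 37.6% |

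With a Wald z-test instead of t, the loss at a 0.1 SD gap is similar: 78.4% against 82.1% (ICC 0.01) and 42.9% against 44.9% (ICC 0.04).

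**Step 4: direction of the error.** At ICC 0.01 and a gap of 0.2 SD, the actual spread of the estimate is 0.0702 without ACO and 0.0687 with it, so the excess lies in the reported standard error. In the same setting without the practice-size covariate, type I error falls from 5.0% to 1.5%.

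**Step 5: if the 4:4 balance breaks.** If the analysis groups were recut so that the high group had 5 practices from one ACO and 3 from the other, with the reverse in the low group, the comparison without ACO would carry (5/8 − 3/8) = 0.25 of the gap. A 6:2 split carries 0.5 of it.

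**Step 6: how large a gap is realistic.** If Latino share were the only route, the ACOs differ by 55 − 8 = 47 points. A 0.1 SD gap then needs a Latino/non-Latino difference of 0.1/0.47 = 0.21 SD after adjustment, and a 0.2 SD gap needs 0.2/0.47 = 0.43 SD. The smaller gap is the more realistic one.

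**The case against.** **No gap is documented.** This stands. The text on Latino patients concerns clinical goals, not physical or social function or experience of care. Commercial share is close (70% and 68%). PAM is already in the outcome equations, so any ACO difference that runs through activation is removed. The gain at 0.1 SD is small.

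**The plan leaves room for ACO.** Also true, which makes this a gap in specification rather than a wrong model. But the covariates named at each step do not include it.

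**The reach is narrow.** This stands too. A stable gap in levels largely cancels in the wave-to-wave comparison of Aim 3 and in the change models of Aims 2 and 4. The Aim 1 equation for PAM itself is a plain linear regression, where a 0.2 SD gap changes the standard error by a factor of only √(1 + 0.04/4) = 1.005. For the clinical measures, EHR data are expected for most sampled patients, but the equation contains PAM. It can therefore use only survey respondents, about 132 per practice at wave 1, so power figures at larger numbers per practice do not apply.

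**Stronger readings.** A reader might infer that leaving out ACO confounds the high-low comparison or produces false positives. With four and four in each ACO it does neither. The exception within that balance is a practice size that differs by both ACO and PA&E group: about 7% of the gap leaks in if size differs by 0.5 SD on each, which is 0.007 SD at a 0.1 SD gap. A reader might also infer that the stated 0.90 power is wrong. That figure is for change in systolic pressure, where a stable gap cancels, and its ICC comes from HealthCare Partners practices alone, so it contains no variance between ACOs.

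**Conclusion.** The point holds for the Aim 1 multilevel models of patient-reported outcomes, patient experience and clinical measures, and for the precision of their refits at each wave under Aim 3. Selection is stratified by ACO and these models do not name it. Any remaining ACO gap in levels inflates the reported high-low standard error: by about 3 to 7% at 0.1 SD and 11 to 28% at 0.2 SD. Including ACO then recovers roughly 1 to 4 or 7 to 19 points of power. With no gap it costs under 1 point, and at 0.05 SD it is about neutral. These figures rest on assumed gaps, the plan's ICC range and response rates, an effect of 0.20 SD and an alpha of 0.05.

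The error is conservative while the 4:4 balance holds. The plan does not say that the high/low variable in the analysis is the group fixed at selection. If it is not, the balance can break and part of the ACO gap becomes bias. Priority: minor to moderate.

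**What to change.** 1. Add ACO as a two-level fixed effect to the Aim 1 outcome models and their Aim 3 refits, where it matters most. For consistency, add it to the change models of Aims 2 and 4 as well; the change in PA&E used in Aim 4 is not balanced by ACO.
2. Define high/low in the analysis as the group under which each practice was selected, in place of a new cut of the response distributions. This keeps the balance whether the quartiles were formed within each ACO or across both.

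The cost is two sentences in the analysis section and one practice-level degree of freedom (13 to 12 with practice size in the model; critical t from 2.160 to 2.179). No new data are needed.

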We will randomly select 273 patients with diabetes and/or CVD from each of the 16 practices. Given the 16 practice sites, we will have data from 4,368 patients. We will follow them as cohorts over a two-year period. See Figure 2 below for selection design. Patients will complete the 13-item PAM measure, patient-reported outcomes (PROMIS), and experience of care measures between 7-12 months and again between 19-24 months. We will obtain measures of blood pressure, HbA1c and LDL-C at 12 months and 24 months from the EHR. We expect a 50% response rate to the first survey round and 65% response rate to the second survey round, with 3% undeliverable and 20% attrition over the two-measurement period, leaving 1102 patients, or 69 patients per practice, available for analysis. The calculations provided

PRINCIPAL INVESTIGATOR (LAST, FIRST, MIDDLE): [name]

below for the PROMIS self-reported measures and for blood pressure provide evidence of sufficient statistical power to detect meaningful differences between practices on these key variables of interest.

Figure 2. Selection and engagement of ACO practices, patients, and teams

Study Sites

Advocate Health Care (Advocate) and Advocate Physician Partners (APP) operate both a commercial and a Medicare ACO. In 2011, Advocate joined with its largest commercial insurance partner to create AdvocateCare, providing care to 370,000 covered lives. In 2012, Advocate was chosen to participate in the Medicare Shared Savings Program (MSSP), becoming one of the largest Medicare ACOs in the country, serving an estimated 106,000 Medicare beneficiaries.

HealthCare Partners ACO (HCP) was formed in 2010 as one of the early Dartmouth-Brookings demonstration ACOs⁴⁶. They hold both CMS and private payer risk-based contracts collectively accountable for 50,000 lives. They serve high proportions of Medicaid patients in low-income communities who tend to face many social and financial barriers to self-management in care for diabetes and CVD. Approximately 55% of HCP's Southern California patients are Latino. Table 2 compares key characteristics of the partnering ACOs. Both Advocate and HCP are highly committed to this study as indicated by their letters of support and related materials in this proposal.

Table 2. Summary of key characteristics of the two participating ACOs

	Advocate ACO	HealthCare Partners ACO

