To project the sample size requirements given 16 practices (8 high PA&E and 8 low PA&E), we estimated the design effect (DE) to account for the clustering of patients within practice sites. While PROMIS data from participating ACO patients are presently unavailable, recent studies of change over time on the PROMIS physical functioning measure informed our sample size estimates for the PROMIS measure⁴⁷. Having been selected using item-response theory (IRT) methods and extensive testing, the PROMIS physical functioning measure is a precise measure that is sensitive to small changes in physical functioning over time. Given the published estimates and a range of design effect estimates (intraclass correlation (ICC)=0.01-0.04) to account for the clustering of patients within practices, a clinically meaningful change (e.g.,

PRINCIPAL INVESTIGATOR (LAST, FIRST, MIDDLE): [name]

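### Aim 3 compares coefficients from separate models at each wave; the waves share practices and patients, so this gives no valid standard error for the change in the PA&E effect, and one joint model would.

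*Combined protocol and SAP*

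**What the plan says.** The aim is "To assess the stability of the PA&E-outcome relationship over two measurement periods at the individual and practice-level" (Analysis Section, Aim 3). The method, once both waves are in, is: "We will compare the regression coefficients for models at each wave to examine differences in associations of the independent variables". Each wave is modelled as its own cross-section. The section gives no standard error for the difference, test, interval, joint model or criterion for calling the relationship stable.

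The Research Plan describes the sample: "We will randomly select 273 patients with diabetes and/or CVD from each of the 16 practices", and "We will follow them as cohorts over a two-year period". It gives the expected response and attrition, "leaving 1102 patients, or 69 patients per practice, available for analysis". Patient Selection makes clear that the 1,102 are patients with two time points.

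The Aim 1 models, which Aim 3 appears to reuse at each wave, allow for patients clustered within practices. They name no level for repeated measurements on one patient. High or low PA&E is a category set from the baseline practice survey.

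**The concern.** The quantity Aim 3 needs is the change in the PA&E coefficient from wave 1 to wave 2, with its uncertainty. Its variance is Var(b1) + Var(b2) - 2 Cov(b1, b2). Shared practices and patients make the covariance positive, and two separate fits do not estimate it. A reader of two coefficients side by side has two obvious shortcuts, and both can mislead. Combining the two standard errors as if independent makes the comparison too conservative, so a real change may be called stability. Noting at which wave the effect is significant can make a constant effect look unstable.

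A second issue is who is in each model. On the plan's rates about half of the wave 1 respondents do not return. If each model uses whoever answered, a changed coefficient may reflect a changed sample. The plan does not say whether the wave 1 model uses all wave 1 respondents or only those with both waves.

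**Working it through.** **Inputs from the documents.** 16 practices, 8 high and 8 low; 273 patients per practice (4,368); 3% undeliverable; response 50% then 65%; 20% attrition (Research Plan); ICC 0.01-0.04 for PROMIS and 3-5 points as a meaningful change (Patient Selection).

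**Assumed, not in the documents.** Outcome SD 10; within-patient correlation rho 0.5-0.8; correlation r of practice effects across waves 0.5-1.0; all wave 2 respondents also answered wave 1.

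**Step 1: the plan's own figure.** 4368 x 0.97 x 0.50 x 0.65 x 0.80 = 1,101.6, or 68.9 per practice, which reproduces 1,102 and 69. The first part of the chain, 4368 x 0.97 x 0.50, gives 2,118 wave 1 respondents (132.4 per practice). So 0.65 x 0.80 = 52% return and about 1,017 patients have wave 1 only.

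**Step 2: standard error of the difference.** With m1 = 132.4, m2 = 68.9, between-practice variance B = 100 x ICC and within-practice variance W = 100 - B:

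- Var(b1) = (2/8)(B + W/m1); Var(b2) = (2/8)(B + W/m2)
- Cov(b1, b2) = (2/8)(r B + rho W/m1)

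At ICC 0.01, Var(b1) = 0.437 and Var(b2) = 0.610, so the independence SE is sqrt(1.046) = 1.02. With r = rho = 0.5, Cov = 0.218 and the SE allowing for correlation is sqrt(1.046 - 0.437) = 0.78.

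| ICC | Independence SE | Correct SE over the range | Overstatement | Correlation of b1, b2 |
|---|---|---|---|---|
| 0.01 | 1.02 | 0.50-0.78 | 1.3-2.1 | 0.42-0.77 |
| 0.04 | 1.59 | 0.49-1.16 | 1.4-3.3 | 0.47-0.91 |

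A nominal 5% test using the independence SE would run at about 1% or less.

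**Step 3: what could be missed** (normal approximation, two-sided 5%). With the independence SE, a change is declared only beyond 1.96 x 1.02 = 2.0 points (ICC 0.01) or 1.96 x 1.59 = 3.1 points (ICC 0.04). A true change of 3 points would therefore usually be found at ICC 0.01, but missed more than half the time at ICC 0.04. With the correct SE at ICC 0.04 the threshold is 1.96 x 0.49 = 1.0 to 1.96 x 1.16 = 2.3 points.

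**Step 4: significance wave by wave.** 20,000 simulated studies, the same true effect at both waves, r = 0.8, rho = 0.7, t tests on 14 df. Share significant at exactly one wave:

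| True effect | ICC 0.01 | ICC 0.02 | ICC 0.04 |
|---|---|---|---|
| 0.25 SD | 15% | 22% | 25% |
| 0.3 SD | 5% | 13% | 22% |
| 0.4 SD | 0.3% | 2% | 10% |
| 0.5 SD | 0% | 0.1% | 2% |

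At SD 10, the plan's 3-5 points correspond to 0.3-0.5 SD.

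**Step 5: different respondents.** 400 simulated studies per case, true coefficient 3 points at both waves, ICC 0.02, rho = 0.7, about 52% returning. Mean apparent change in points:

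| Dependence of return on wave 1 score | Separate models | Two-wave patients only | Joint likelihood |
|---|---|---|---|
| None | -0.05 | -0.01 | -0.02 |
| Same in both groups (log-odds 0.5 per SD) | -0.13 | 0.06 | 0.00 |
| Low PA&E group only (0.5) | -1.64 | 0.69 | 0.01 |
| High PA&E group only (0.5) | 1.48 | -0.66 | -0.03 |

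**Step 6: is an interaction term enough?** No. An ordinary pooled regression with a wave-by-PA&E term and no patient effect returned exactly the separate-model difference (-0.890 in both).

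**The case against.** The strongest reply is that Aim 2 already contains the needed analysis. It models change in outcomes with site random effects and PA&E as a predictor. For patients with both waves and no covariates, the PA&E term in a change-score model is the wave-by-PA&E term. That is correct, and it narrows the gap. It does not close it: Aim 2 conditions on baseline PAM, its displayed equations show no change score, it is limited to two-wave patients, and nothing ties it to Aim 3. Aim 4 mentions an interaction term, but its equations regress change on change and contain neither a wave term nor an interaction.

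Separate fits can also be compared validly, for example by resampling practices. That stands, but the plan does not propose it.

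Three stronger readings are tempting and should be resisted:

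- A reader might infer that the plan judges stability by significance at each wave. It speaks of comparing coefficients and states no criterion, so Step 4 describes a risk, and one that nearly disappears at 0.5 SD.
- A reader might infer that every wave 2 respondent is a wave 1 respondent and that wave 2 totals 1,102. The documents give 1,102 as the number with two time points. Sources of Materials has selected patients surveyed again at 19-24 months without restricting this to earlier responders. Nesting is suggested by multiplying the rates, but it is not stated.
- A reader might infer that dropout will distort the comparison. Step 5 shows little distortion unless dropout depends on outcome differently in the two PA&E groups. EHR measures are expected for most of the 4,368, although PAM as a covariate limits those models to survey respondents.

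**Conclusion.** The point holds as a gap in the method for one of six aims; it does not touch the central comparison. Separate wave models cannot supply the uncertainty of the change that Aim 3 asks about. Any positive cross-wave correlation makes the independence standard error too large; the 1.3 to 3.3 range depends on the assumed correlations and on nesting of wave 2 in wave 1, while the points figures also depend on SD 10. The practical loss is greatest towards ICC 0.04; at ICC 0.01 a 3-point change would usually still be seen. Bias from dropout is conditional: about 1.5 points in the one-sided cases simulated, near zero otherwise. The plan is silent on inference here and does not state a wrong rule, but the remedy is cheap enough to be worth adopting before wave 2 data are analysed.

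**What to change.** For Aim 3, replace the wave-by-wave comparison with one stacked mixed model on all available data from both waves:

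- Random effects for patient, practice and practice-by-wave, or an equivalent within-patient covariance.
- Fixed effects for wave, baseline high/low PA&E, wave-by-PA&E, practice size and casemix. Add wave-by-PAM where the PAM coefficient is compared.
- Small-sample degrees of freedom suited to 16 practices.
- A logistic version for the binary control measures (blood pressure, HbA1c, LDL-C).

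Report the wave-by-PA&E estimate with its confidence interval as the measure of stability; a non-significant difference should not be read as stability. State the missing-data assumption. In Step 5 the joint likelihood removed the bias because return depended only on the observed wave 1 score. Repeat the analysis in two-wave respondents as a sensitivity analysis, noting that this does not by itself remove dropout bias: it left about 0.7 points, with the opposite sign, in the one-sided cases. Say how the result relates to Aim 2's change model.

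The cost is slightly more modelling work, with no new data, visits or patients.
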